## **5.0 DRUG/DEVICE/BIOLOGIC AGENT INFORMATION**

The PBM treatment will be administered via the Food and Drug Administration (FDA) approved THOR Model LX2M unit (THOR Photomedicine Ltd, Chesham, UK). The THOR LX2M is a red and near infrared light emitting diode (LED) licensed for management and treatment of inflammation and tissue repair. The THOR Model LX2M has a 69 Diode LED Cluster Probe (34 X 660nm 10mW, 35 X 850nm 30mW: 1390mW total power output) at an irradiance of 50mW/cm^2. The unit is portable and can be carried to each patient room. Cleaning will be according to hospital equipment policy.

## Safety

The PBM poses less risk than that associated with the class IV surgical laser used in dentistry. While the potential hazards are ocular, the PBM are class 3B lasers and emit divergent beams with the ocular risk diminishing with distance.[25] Recommendations include avoiding direct aim of the laser into the eye and the use of safety spectacles for use with laser therapy. The safety spectacles will be prescribed according to age, with the adjustable Ibis Infant eye protection for patients less than 1 year of age and the adjustable kids laser safety goggles for the young child. Patients, staff, and observers must wear laser safety glasses while

St. Jude Children's Research Hospital

IRB NUMBER: 19-0225

IRB APPROVAL DATE: 01/28/2021

PBM is in use. Specific contraindications are listed below:

## **Contraindications to PBM**

### *Eyes*

THOR lasers have divergent beams but are potentially harmful if viewed directly from a distance of less than 1.1 meters. Patient, practitioner and observers should wear THOR laser safety glasses when the laser is in use.

## **Relative contraindications / precautions**

### *Cancer*

Do not use PBM over any known malignant lesions unless:

1. for pain relief during the terminal stages of the illness, but only with their physicians permission.
2. For cancer therapy side effects (e.g. oral mucositis, radiation dermatitis, etc.),

### *Pregnancy*

There is no evidence of harm to an unborn baby however there are no safety tests either, so for medical legal reasons we recommend not treating directly over the developing fetus. It may be used on the pregnant woman for the treatment of back pain etc.

### *Thyroid*

There is no evidence of harm and there is some evidence of benefit for treating Hashimoto's thyroiditis with PBM. It is conceivable that a high intensity laser treatment direct to the thyroid might (temporarily) stimulate (or inhibit) some thyroid activity. The THOR LED treatments are however relatively low intensity and far less likely to trigger any adverse events when treating that region of the neck.

### *Tattoo*

Treatment over a tattoo with higher irradiance laser may cause pain as the dye absorbs the laser energy and gets hot. If treatment is painful remove treatment probe from contact and treat ~15mm from surface of skin.

### *Hair on the head*

Treatment on the head and neck with high irradiance laser may cause pain as the melanin in the fine superficial hair follicle absorbs a lot of the laser energy. If treatment is painful remove treatment probe from contact and treat ~15mm from surface of skin.

### *Very dark skin*

Occasionally some people with very dark skin feel an unpleasant amount of heating. If treatment is painful remove treatment probe from contact and treat ~15mm from surface of skin.

### ***Cleaning of Laser Between Patients***

All laser heads will be covered with clear disposable dental sleeves that are approved for use with the LLLT and in dentistry. At treatment completion the sleeves will be discarded and all laser heads, laser box and all cords will be cleaned with disinfectant wipes (Sani-Cloth) and allowed to air dry in between each patient, per discussion with infectious disease.

## **6.0 REQUIRED EVALUATIONS, TESTS, AND OBSERVATIONS**

### **6.1 Pre-Study Evaluations**

Each participant will have a pre-transplant dental assessment to assess for caries, periodontal disease and mouth ulcerations, as well as pre-transplant oral and nasal cultures as per protocol.

### **6.2 Response Evaluations During Therapy**

#### *Parent Satisfaction*

After the initial LLLT treatment, a parent-reported satisfaction survey will be administered via paper questionnaire. Parent satisfaction will be reported by parents on a 5-point Likert scale to questions adapted from a parent satisfaction survey used in a study regarding child life services in pediatric imaging [26]. Parents will be asked to rate their level of satisfaction on 10 items, with 1 = Strongly Disagree to 5 = Strongly Agree. An additional marker of “not applicable (N/A)” will be available as a response option for parents who respond to the survey and did not receive a child life play-based preparation. Higher scores indicate higher satisfaction.

#### **Parent Satisfaction Survey Items**

1. The procedure was explained using language my child could understand.
2. My child’s emotional needs were met.
3. Staff showed concern for my child’s comfort.
4. I knew what to do to help my child.
5. Staff showed concern for my questions and worries.
6. Staff respected my knowledge of my child.

7. I am satisfied with the care provided to my child.
8. The child life intervention was helpful for my child's understanding in the procedure.
9. Staff were friendly and helpful.
10. Staff worked together well to care for my child.

### *Pain and Oral Function Assessment*

After the 6-minute laser/ treatment session the child or parent proxy will complete the mucositis evaluation scale which includes self-report oral function specific to ability to swallow, eat and drink, as well as the patient's self-reported need for medication specific to mouth pain. The evaluation of mucositis can be completed in less than 5 minutes and is a validated inventory, Children's International Mucositis Evaluation Scale which has been used for mucositis in pediatric HCT. [27] The scale has test-retest reliability with  $r>0.8$  for all respondent types. See attached. The scale is available in English, Spanish and Portuguese.

The study staff will maintain a treatment log for each participant. Data collected will include: days on PBM protocol, days treatment received, total cumulative dose defined as single treatment dose multiplied by the number of treatment sites (up to 6 in total) for each treatment session.

Mucositis will be graded according to the Common Toxicity Criteria for Adverse Events version 5: Grade I patient is asymptomatic or with mild symptoms, no intervention, Grade II patient has moderate pain, no interference with oral intake and a modified diet, Grade III patient has severe pain, interfering with oral intake, Grade IV life-threatening, Grade V death.

In addition to the study staff assessment, the clinical assessment of mucositis and pain from the daily APN and physician physical assessment will be collected.

### *Chart Abstraction*

The patient's age, sex, primary diagnosis, transplant type, conditioning regimen, radiation dose, time to engraftment, days of nutritional support, utilization of pain medication, and results of positive oral, nasal and blood cultures during transplant.

## 6.3 Off-Study Evaluations

1. Patients are off-study on last day (Day +20 or engraftment or absence of mucositis)

of PBM administration except for patients undergoing autologous tandem transplant will discontinue treatment with mucositis resolution and then resume light therapy with second transplant. Thus, these patients will remain on study until resolution of mucositis after second transplant. Therefore, will not reconsent with the second transplant, parents and patient may refuse if desired

## **7. CRITERIA FOR REMOVAL FROM PROTOCOL THERAPY AND OFF-STUDY CRITERIA**

### **7.1 Off-study criteria**

#### **7.1.1 Death**

#### **7.1.2 Request of the Patient/Parent**

#### **7.1.3 Discretion of the Study PI, such as the following**

- The researcher decides that continuing in the study would be harmful
- A treatment is needed that is not allowed on this study
- The participant misses > 3 consecutive days of PBM the data cannot be used in the study
- The participant's condition gets worse
- New information is learned that a better treatment is available, or that the study is not in the participant's best interest
- Study evaluations are complete

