## **8. SAFETY AND ADVERSE EVENT REPORTING REQUIREMENTS**

### **8.1. Adverse Events (AEs)**

Adverse events will be monitored from the time of first study intervention, Day 1 of conditioning until Day +20 or engraftment. Participants will be instructed to report all AEs during the study and will be assessed for the occurrence of AEs throughout the study.

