### 8.3. Handling of Adverse Events (AEs) and Deaths

**Recording of Adverse Events and Serious Adverse Events:** Skin will be assessed and recorded daily for erythema or breakdown prior to light application.

**Reporting Adverse Events and Serious Adverse Events:** The St. Jude PI, upon awareness of an event, will determine the seriousness of AEs and ensure that all UPs are entered into the electronic submission system (iRIS) within 10 days. All (pertinent, as in recording above) AEs, serious or not, will be recorded in a log, spreadsheet, or report and submitted to the St. Jude IRB at the time of continuing review.

**Reporting of Unanticipated Problems (UPs):** The St. Jude PI will refer to St. Jude Human Research Protection Program (HRPP) Policy 01.720 for specifics on the reporting of unanticipated problems to the St. Jude IRB. The St. Jude IRB reports UPs to BIMO as per 21 CFR 56. The UP link follows: [\[REDACTED\]](#)

Deaths meeting reporting requirements are to be reported immediately to the St. Jude IRB, but in no event later than 48 hours after the investigator first learns of the death.

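### Section 7 lists only reasons to leave the study, so a child whose PBM is stopped for harm, a disallowed treatment or worsening may drop out of AE follow-up and the primary grade 3 count

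*Combined protocol and SAP*

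**What the plan says.** The title of Section 7 promises criteria for removal from protocol therapy and for leaving the study. Its only subsection, 7.1, gives off-study criteria. Section 7.1.3 lists examples for PI discretion, among them "The researcher decides that continuing in the study would be harmful", "A treatment is needed that is not allowed on this study" and "The participant's condition gets worse". Another item reads "The participant misses > 3 consecutive days of PBM the data cannot be used in the study".

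Other sections bear on the same children:

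- **Section 6.3** puts the scheduled off-study date at the last day of PBM. Its one exception keeps tandem autologous patients on study between courses.
- **Section 4.1** sets aside the data of acutely ill children who miss 4 consecutive days, and replaces them to reach 66 evaluable. It defines the binary grade 3 endpoint from day 1 of conditioning to Day +20 or engraftment. It also provides for days without treatment, with reasons recorded.
- **Section 8.1** says "Adverse events will be monitored from the time of first study intervention, Day 1 of conditioning until Day +20 or engraftment", and then "Participants will be instructed to report all AEs during the study and will be assessed for the occurrence of AEs throughout the study".
- **Section 8.3** says "Skin will be assessed and recorded daily for erythema or breakdown prior to light application".
- **Section 6.2** says "After the 6-minute laser/ treatment session the child or parent proxy will complete the mucositis evaluation scale". It also collects the daily clinical mucositis assessments.
- **Section 10.2.2** compares the matched groups over the same window, to engraftment or Day +20.

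**The concern.** Harm, a disallowed treatment and worsening are normally reasons to stop an intervention while follow-up goes on. Here they appear only as reasons to leave the study, and no section says what is collected or counted afterwards.

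Two things are at stake. The first is safety: the AEs that follow a stop for harm are the ones a safety summary most needs. The second is the primary endpoint. Worsening is not defined, and it could include developing mucositis or illness that accompanies it. PBM starts on day 1 of conditioning, whereas Section 2.2 reports a median mucositis onset at this site of Day 3 after infusion (range -3 to 9), so a stop can come before the event. In a single-arm comparison with a historical rate, losing children who were heading for grade 3 lowers the observed rate and makes PBM look better than it is.

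**Working it through.** **Does any text close the gap?** The Section 8.1 window has no exception for stopped PBM. Its next sentence, however, ties reporting and assessment to the study, and Section 7.1 takes these children off it. The skin check and the patient-reported scale are each tied to a PBM session, so neither has a stated trigger once sessions end. Clinical staff grade mucositis daily as routine care (Section 4.1), so a later grade 3 event is probably in the chart; what is missing is a rule to collect and count it. Neither Section 4.1 nor Section 7.1.3 says whether a stop ordered by the PI counts as missed days.

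**Inputs from Section 10.1.** Historical sample 66/93 (71%); H0 rate 0.71, H1 rate 0.51; looks at n = 40 (efficacy 20, futility 29) and n = 66 (efficacy 38); attained type I error 0.048 and power 0.813.

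**Reproducing the plan's figures.** The critical values are not printed, so I used

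z = [arcsin√(x/n) − arcsin√(y/93)] / √(1/(4n) + 1/(4·93)),

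with y drawn from Bin(93, 0.71) and all outcomes enumerated exactly. The cut-offs were tuned to the plan's H0 crossing probabilities: stage 1 efficacy z ≤ −2.150, stage 1 futility z ≥ 0.010, final efficacy z ≤ −1.697. At y = 66 these return the printed 20, 29 and 38.

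| | Stage 1 efficacy | Stage 1 futility | Stage 2 efficacy | Total efficacy |
|---|---|---|---|---|
| H0, computed | 0.0150 | 0.508 | 0.0326 | 0.0477 |
| H0, plan | 0.015 | 0.508 | 0.033 | 0.048 |
| H1, computed | 0.525 | 0.015 | 0.291 | 0.815 |
| H1, plan | 0.526 | 0.015 | 0.288 | 0.813 |

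**Illustration.** The documents give no stop rate. Assume PBM has no effect, and that stopped children are excluded and replaced under the missed-days rule. Let f be the fraction of would-be grade 3 children removed before the event, and g the fraction of the others. The rate among evaluable children is

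p = 0.71(1−f) / [0.71(1−f) + 0.29(1−g)].

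For f = 0.10 and g = 0 this is 0.639/0.929 = 0.6878. The number removed on the way to 66 evaluable is 66r/(1−r), with r = 0.71f + 0.29g.

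| f | g | p | Children removed | Type I error |
|---|---|---|---|---|
| 0 | 0 | 0.7100 | 0 | 0.048 |
| 0.02 | 0 | 0.7058 | 0.95 | 0.054 |
| 0.05 | 0 | 0.6993 | 2.4 | 0.064 |
| 0.10 | 0 | 0.6878 | 5.0 | 0.086 |
| 0.10 | 0.05 | 0.6987 | 6.2 | 0.065 |
| f = g | | 0.7100 | any | 0.048 |

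**Dependence on the form of the test.** With g = 0 and f = 0.02, 0.05 and 0.10:

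- Pooled z tuned in the same way: 0.048 rises to 0.054, 0.064 and 0.086.
- Untuned pooled z at the printed boundaries: 0.043 rises to 0.049, 0.058 and 0.079.
- Printed boundaries read as differences from 66/93: 0.036 rises to 0.041, 0.050 and 0.069.

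The direction is the same in all of them. At f = 0.02 the change is small compared with the uncertainty about the unprinted critical values.

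**The case against.** The strongest reply is that the windows are already fixed and none depends on continuing PBM. Section 8.1 monitors AEs to Day +20 or engraftment; Sections 4.1 and 10.2.2 use the same end point; Section 4.1 counts days on protocol separately from days treated; and Section 10.2.1 computes the primary percentage with no exception for early stops. Removal under Section 7.1.3 is discretionary, so a PI may stop PBM and keep the child on study. The study is rated low risk for monitoring, and grading continues in the chart regardless.

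Much of this stands. A reader might infer that AEs after a stop are certainly lost; the documents do not support that, because the Section 8.1 window, read alone, could cover these children. A reader might also infer that Section 7 by itself raises the type I error to 0.086. It does not. Every inflated figure above comes from the missed-days exclusion and replacement, applied to stopped children on an assumption the text leaves open, and with removal related to mucositis risk. A child who has already reached grade 3 when PBM stops has had the event. Nor does any section say that a stopped child is scored as free of grade 3, so I give no figures for that reading.

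What the reply does not supply is a sentence saying that a child taken off study under Section 7.1.3 is still followed and counted. Section 6.3, which ends the study with the last PBM day, and the bar on using data after more than 3 missed days both point the other way.

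**Conclusion.** The gap is real and is worth closing as a cheap improvement. For AEs it is an ambiguity between a stated window and an off-study rule. For the primary endpoint, following the stated rules can drop worsening children before grade 3, which would favour PBM against 71%. The size is unknown and may be small. The rise from 0.048 to 0.054–0.086 holds only if stopped children are excluded and replaced and if 2% to 10% of would-be grade 3 children, and no others, are removed. The effect is nil if removal is unrelated to risk or if these children are counted from the chart. Confidence is medium, because no stop rate is given.

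**What to change.** 1. Split Section 7 into off-treatment and off-study criteria, and move harm, disallowed treatment and worsening to off-treatment. Whether PBM continues remains a clinical decision.
2. Unless consent is withdrawn or the child dies, keep collecting AEs and the routinely charted mucositis grade to Day +20 or engraftment (for autologous patients, to their protocol end point).
3. State in Section 6.3 that an early PBM stop does not move the off-study date.
4. Count every allogeneic child who started PBM and was stopped early in the primary grade 3 result.
5. Align Sections 4.1 and 7.1.3 so that a permanent stop, including one for acute illness, triggers neither exclusion nor replacement. Exempting only stops ordered by the PI would leave the acute-illness exclusion in Section 4.1 in force, and evaluability would then depend on how a stop is labelled.
6. If wanted, keep a result that excludes children with 4 or more consecutive missed days as a sensitivity analysis.

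The cost is amendment wording and a few more chart days per stopped child. The PBM rate may come out less favourable.

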## **8. SAFETY AND ADVERSE EVENT REPORTING REQUIREMENTS**

### **8.1. Adverse Events (AEs)**

Adverse events will be monitored from the time of first study intervention, Day 1 of conditioning until Day +20 or engraftment. Participants will be instructed to report all AEs during the study and will be assessed for the occurrence of AEs throughout the study.

### **8.2. Definitions**

**Adverse Event (AE):** Any untoward medical occurrence associated in a study participant after the first intervention on study. Adverse Events grade 1-4 will be graded by the NCI CTC AE version 5.0.

**Serious Adverse Event (SAE):** Any adverse event temporally associated with the subject's participation in research that meets any of the following criteria:

\* results in death; \* is life-threatening (places the subject at immediate risk of death from the event as it occurred); \* requires inpatient hospitalization or prolongation of existing hospitalization; \* results in a persistent or significant disability/incapacity; \* results in a congenital anomaly/birth defect; or \* any other adverse event that, based upon appropriate medical judgment, may jeopardize the subject's health and may require medical or surgical intervention to prevent one of the other outcomes listed in this definition.

### 8.3. Handling of Adverse Events (AEs) and Deaths

**Recording of Adverse Events and Serious Adverse Events:** Skin will be assessed and recorded daily for erythema or breakdown prior to light application.

**Reporting Adverse Events and Serious Adverse Events:** The St. Jude PI, upon awareness of an event, will determine the seriousness of AEs and ensure that all UPs are entered into the electronic submission system (iRIS) within 10 days. All (pertinent, as in recording above) AEs, serious or not, will be recorded in a log, spreadsheet, or report and submitted to the St. Jude IRB at the time of continuing review.

**Reporting of Unanticipated Problems (UPs):** The St. Jude PI will refer to St. Jude Human Research Protection Program (HRPP) Policy 01.720 for specifics on the reporting of unanticipated problems to the St. Jude IRB. The St. Jude IRB reports UPs to BIMO as per 21 CFR 56. The UP link follows: [\[REDACTED\]](#)

Deaths meeting reporting requirements are to be reported immediately to the St. Jude IRB, but in no event later than 48 hours after the investigator first learns of the death.

## 9. DATA COLLECTION, STUDY MONITORING, AND CONFIDENTIALITY

### 9.1 Data Collection and Confidentiality

*All data will be kept confidential and will be maintained in a secure, password protected database accessible only by study personnel. Study numbers will be assigned to each patient so that the patient's medical record number will not be used as the identifying number. All data will be kept confidential and stored in locked files inside locked offices. The site PI, study team, and staff of the*

St. Jude Children's Research Hospital  
IRB NUMBER: 19-0225  
IRB APPROVAL DATE: 01/28/2021

*CPDMO at SJCRH will have access to the original data forms. Participants may decline without any negative repercussions whatsoever. Those refusals will be documented in the research record and examined for any possible patterns in patient/parent demographic variables.*

## 9.2 Study Monitoring

This study is considered low risk for monitoring purposes. The Principal Investigator (PI) and study team are responsible for ensuring participant eligibility and protocol compliance. The study team will hold meetings as needed to review case histories or quality summaries on participants and will generate minutes which are signed by the PI.

A quality review for form completeness will be performed on the informed consent forms of 100% of St. Jude participants by Clinical Trials Operations (CTO) personnel.

CTO will review up to 10% of the study participants annually for life status, status on study, and the appropriateness of the informed consent and eligibility processes. The monitor will annually verify regulatory documentation pertinent to the study, all Serious Adverse Event reports, and Age of Majority consenting on all study participants. The plan for monitoring may be revised over time, to adapt monitoring frequency and/ or intensity to a changing environment when appropriate (for example: new safety signals; positive history of compliance; all participants are in long term follow-up; or the enrollment period has ended). The Monitor will generate a formal report which is shared with the Principal Investigator, study team, and the Internal Monitoring Committee (IMC).

Protocol continuing reviews by the Institutional Review Board (IRB) and Scientific Review Committee (CT-SRC) will occur at least annually. In addition, Unanticipated Problems and/or Serious Adverse Event reports are reviewed by the IRB.

# 10. STATISTICAL CONSIDERATIONS

## 10.1 Sample Size

A review from June 2015 to May 2019, identified 93 first allogeneic transplant patients with similar conditions, and 66 (71%) of them developed grade 3 or above oral mucositis. With an estimated clinically meaningful effect size of 20% for PBM, the estimated percentage of patients who will receive PBM and develop grade 3 oral mucositis is 51%.

St. Jude Children's Research Hospital  
IRB NUMBER: 19-0225  
IRB APPROVAL DATE: 01/28/2021

We will use the two-stage one-arm design with historical controls to monitor both efficacy and futility. The complete historical control sample will be used in both the interim analysis and final analysis. The test statistic in Chang et al [28] treats the historical control sample as if they are the control arm in a two-arm design. Given the relatively small sample size, we did not use the asymptotic distribution of the test statistic. Instead, we used Monte Carlo methods to estimate the sampling distribution of the test statistic under null and alternative hypotheses by 100,000 Monte Carlo data sets. The simulation program is written in R.

The rules of which accommodate both efficacy and futility. The null hypothesis is  $p_0=0.71$ ; the alternative hypothesis is  $p_1=0.51$ ; The type-I error rate = 0.05 and power 0.8 are used.. The detailed information about the two-stage design is shown in the following table. The attained type-I error rate and power are 0.048 and 0.813, respectively.

Loo k #	n	Boundari es		Boundary Crossing Probability (Incremental)			
				Under H0		Under H1	
		Efficac y	Futilit y	Efficac y	Futilit y	Efficac y	Futilit y
1	40	20	29	0.015	0.508	0.526	0.015
2	66	38	39	0.033	0.444	0.288	0.172
Total				0.048	0.952	0.813	0.187

The expected sample size under null and alternative hypotheses is 56 and 51, respectively. In the historical data between July 2015 and May 2016, 24 patients received allogeneic HCT. We estimate that study accrual of 66 transplant patients will be completed in 31 months after study activation.

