## 10.2 Statistical Analyses

### 10.2.1 Statistical analysis for the primary objective

*To evaluate the feasibility and efficacy of photobiomodulation therapy (PBM) in reducing oral mucositis in children and adolescents at risk for grade 3 oral mucositis undergoing an allogeneic hematopoietic cell transplant (HCT).*

Hypothesis 1: Children and adolescents will receive 75% of the attempted PMB treatment and will be less likely to develop grade 3 oral mucositis from the 1st day of conditioning to day +20 of transplant or engraftment.

Descriptive statistics (counts, percentages, mean, median, standard deviation and interquartile range) and confidence interval will be calculated for the percentage of successful treatment administered, total days on the protocol, days treatment is received, cumulative dose and the number of treatments received at each site.

The count, percentage and confidence interval will be calculated for allogeneic HCT patients who receive PBM and develop Grade 3 mucositis. Whether the percentage of the prospective sample is significantly different from the historical rate is accessed by the monitoring rule in Section 10.1.

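### Section 10.1 prints an expected sample size of 56 under the null, but its own boundary table gives 52.4; the sentence is the likely error

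*Combined protocol and SAP*

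**What the plan says.** Section 10.1 sets out the design: "We will use the two-stage one-arm design with historical controls to monitor both efficacy and futility". The table has one row per look, giving the look number, n, efficacy boundary, futility boundary, and then the probabilities of crossing each boundary, first under the null (0.71) and then under the alternative (0.51). The table heading marks these probabilities as incremental, that is, per look.

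- First look: "1 40 20 29 0.015 0.508 0.526 0.015"
- Second look: "2 66 38 39 0.033 0.444 0.288 0.172"

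The text before the table reports the totals: "The attained type-I error rate and power are 0.048 and 0.813, respectively". The sentence after it reads: "The expected sample size under null and alternative hypotheses is 56 and 51, respectively".

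The method is also described. The test statistic "treats the historical control sample as if they are the control arm in a two-arm design", and its distribution was estimated "under null and alternative hypotheses by 100,000 Monte Carlo data sets".

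**The concern.** In a two-stage design the expected sample size is fixed by the two sample sizes and the probability of stopping at the first look. All three stand in the table, so the sentence beneath it should be reproducible in one line. The alternative value nearly is; the null value is not.

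The expected size under the null tells a reader how many patients the trial would enrol on average if photobiomodulation had no effect. Measured against the maximum of 66, the printed figure implies an average saving of 66 - 56 = 10 patients, and the table implies 66 - 52.4 = 13.6. The mismatch also deserves tracing because the same table is the decision rule for the primary efficacy question. Section 10.2.1 says: "Whether the percentage of the prospective sample is significantly different from the historical rate is accessed by the monitoring rule in Section 10.1".

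**Working it through.** **Inputs (Section 10.1 table).** n1 = 40, n2 = 66, so 26 patients are added if the trial continues. First-look crossing probabilities are 0.015 (efficacy) and 0.508 (futility) under the null, and 0.526 and 0.015 under the alternative.

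**Formula.** E[N] = n1 + (n2 - n1) x (1 - P(stop at first look)).

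**The plan's figures, from its own table.**
- Null: P(stop) = 0.015 + 0.508 = 0.523. E[N] = 40 + 26 x 0.477 = 52.4. Printed: 56. The gap is 3.6 patients, or 6.4% of 56. Not reproduced.
- Alternative: P(stop) = 0.526 + 0.015 = 0.541. E[N] = 40 + 26 x 0.459 = 51.9. Printed: 51. This is consistent with truncation.

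**Stopping probability that 56 would need.** (66 - 56)/26 = 0.385. If 56 was rounded from 55.5 to 56.5, the range is 0.404 to 0.365. If it was truncated from 56 to 57, the range is 0.385 to 0.346. The table has 0.523.

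**Can something harmless explain the gap?**
- Rounding of the table: moving both entries by 0.0005 gives 52.38 to 52.43.
- Monte Carlo error with 100,000 data sets: 26 x sqrt(0.523 x 0.477/100,000) = 0.04 patient.
- Counting only one kind of early stop: efficacy only gives 40 + 26 x 0.985 = 65.6; futility only gives 40 + 26 x 0.492 = 52.8.

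**Is the table coherent?**
- Null: 0.015 + 0.508 + 0.033 + 0.444 = 1.000.
- Alternative: 0.526 + 0.015 + 0.288 + 0.172 = 1.001, which is rounding.
- Type-I error: 0.015 + 0.033 = 0.048, as stated.
- Power: 0.526 + 0.288 = 0.814 against 0.813 stated, again rounding.

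These sums show internal consistency. They do not by themselves show that the simulation was right.

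**Can the key entry be reproduced from the described model?** I enumerated it exactly: 93 controls as Binomial(93, 0.71), 40 treated patients, and a pooled two-sample Z. I assumed that futility means Z <= 0, which Section 10.1 does not state.
- First-look futility is 0.508 under the null and 0.015 under the alternative, both equal to the table to three decimals.
- With 66/93 observed, Z = 0 falls at 40 x 66/93 = 28.4 events, so the first count meeting Z <= 0 is 29 of 40, the printed boundary.
- For efficacy cut-offs from Z = 2.17 to 2.32 (also assumed), E[N] under the null is 52.3 to 52.5.
- The efficacy entries match only approximately. At Z = 2.20 they are 0.0154 under the null (table 0.015) and 0.504 under the alternative (table 0.526).

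**The case against.** The strongest defence of 56 is a different futility convention. If a count of exactly 29 does not stop the trial, a binomial with the null rate fixed at 0.71 (efficacy at 20 or fewer) has a futility probability of 0.359. It then gives an expected size of 56.6 under the null, close to the printed figure. This may be where 56 came from, but it does not rescue the number. It contradicts the tabulated 0.508 and gives 52.6 under the alternative, not 51. The same binomial with futility at 29 or more gives 0.496 and an expected size of 53.0. The final look points the same way. Its boundaries, 38 and 39, are adjacent and every count must be classified, so a count equal to a boundary is naturally read as crossing it.

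A reader might instead infer that the table is wrong, and hence that the stated type-I error and power are unsafe. Some reconstructions seem to invite this: random controls with the cut-off placed at 29/40 against 66/93 give 54.2 to 54.6 under the null and do not match the table. That cut-off is only one choice, however. Placing it at Z <= 0 recovers both futility entries. Nothing in the documents points to a fault in the table.

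It is also fair to say that the consequence is small. No other figure in the plan is derived from the expected sample size, and the printed 56 overstates average enrolment under the null. That limits the weight of the point but does not make the sentence correct.

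**Conclusion.** The point holds as a correction to one number. The expected sample size under the null is printed as 56, and the table gives 52.4. The mismatch is certain, being arithmetic on figures printed next to each other. That the sentence rather than the table is at fault is likely, not proven. It rests on the table's internal consistency and on reproducing its futility entries under the assumed Z <= 0 rule; the efficacy entries were matched only approximately.

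The printed 51 under the alternative is not counted as an error. The point gives no ground for doubting the attained type-I error of 0.048 or the power of 0.813. It does not affect the boundaries, the maximum of 66, or the estimate of 31 months to accrue 66 patients. This is a low-priority correction.

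**What to change.** Check the expected sample sizes against the existing R simulation output. If the table is confirmed, restate the null value in Section 10.1 as about 52 (52.4). For consistency, give the alternative as about 52 (51.9) in the same sentence. While editing, it would help clarity to add that a count equal to a boundary crosses it, if the output confirms that reading.

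The cost is one look at the stored output, or one re-run of the existing program if the output was not kept, and one corrected sentence. No design change follows.
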